### **Determination of Dose-Limiting Toxicities**

The patient population (DLT-Evaluable Set) used for determination of DLTs will consist of all patients enrolled in Dose Escalation who had a DLT, or who received the full dose of DS-6157a in Cycle 1 and completed the DLT evaluation period. Minimum safety requirements will be met if, during Cycle 1 of treatment, the patient receives the planned total dose of DS-6157a, completes all required safety evaluations, and is observed for at least 21 days following the first dose of DS-6157a. Dose escalation to the next dose level will take into account all the safety data as detailed in Section 5.1.1.

Patients who discontinue treatment early due to PD or withdrawal will be asked to have all end-of-treatment safety evaluations performed as described in the protocol (see Section 7.4). If a patient withdraws from treatment during Cycle 1 due to any reason other than a DLT and does not meet the minimum requirements for inclusion in the DLT-Evaluable Set described above, that patient will be replaced.

### **5.1.3 Maximum-Tolerated Dose**

Once the dose escalation stopping criteria are met, the Sponsor will estimate the MTD using a Bayesian logistic regression model (BLRM) and following the escalation with overdose control (EWOC) principle, where the estimated MTD is the dose with the highest posterior probability of the target DLT rate interval of  $16\% < \text{DLT rate} \leq 33\%$  fulfilling the overdose control constraint, i.e. probability of a DLT rate  $>33\%$  (sum of probabilities for excessive and unacceptable toxicity) should be less than 25%. The final MTD will be decided based on considerations of the estimated MTD and on an overall assessment of safety data from subsequent cycles and PK information collected at all different doses tested.

### **5.1.4 Recommended Dose for Expansion**

Based on all available data collected in Dose Escalation (e.g., PK, safety, efficacy, and biomarker data), one dose or regimen, or multiple doses or regimens less than or at the MTD (if attained, or the highest dose evaluated) may be selected as RDE(s) for further evaluation in one

*CONFIDENTIAL*

or more cohort(s) in Dose Expansion. If multiple doses or regimens are selected for Dose Expansion, up to approximately 30 eligible patients may be randomized into each dose or regimen in one or more cohort(s) in Dose Expansion. Alternatively, if a selected RDE is found to be not suitable due to safety or efficacy related reasons during evaluation in Dose Expansion, further enrollment may be continued at a different dose level not exceeding MTD as the new RDE.

Dose Expansion cohorts (Part 2) will then begin at the RDE to further characterize safety and tolerability, the PK profile, and efficacy of DS-6157a. Based on evolving efficacy data from Part 1, additional disease cohorts may be included in Part 2. As one of the options, if there is an objective response in at least one of the patients with GIST who are not candidates for IM or curative intent surgical treatment (e.g., patients without activating KIT or PDGFRa mutations, with PDGFRa D842V mutations, or are KIT negative), an additional Dose Expansion cohort (Cohort 3) of approximately 12 patients of this population may be evaluated at the RDE.

## 5.2 Treatment Duration

DS-6157a will be administered IV on Day 1 of each cycle Q3W. Patients will continue to receive DS-6157a Q3W as long as the patient is deriving benefit from the treatment, until progression of disease (PD) according to RECIST Version 1.1 as assessed by the Investigator, unacceptable toxicity, death, or withdrawal of consent (Section 3.3). Patients may be treated beyond initial radiological progression (according to RECIST Version 1.1) on a case-by-case basis (with agreement from the Medical Monitor), if the Investigator feels that it is in the patient's best interest, the patient re-consents to continue receiving study treatment in a separate consent form, and as long as the patient is deriving benefit from the treatment and all the following criteria are met:

- Absence of clinical symptoms or signs indicating clinically significant disease progression
- No decline in performance status
- Absence of rapid disease progression or threat to vital organs or critical anatomical sites (e.g., CNS metastasis, respiratory failure due to tumor compression, spinal cord compression) requiring urgent alternative medical intervention
- No significant, unacceptable or irreversible toxicities related to study treatment
- Patient agrees to continue protocol-specified assessments and monitoring

Assessments will be performed by the Investigator at screening and every 6 weeks ( $\pm 7$  days) during the first 36 weeks of treatment and every 9 weeks ( $\pm 7$  days) thereafter, as described in the [Assessment Schedule](#) and in Section 7.3. After treatment discontinuation, patients will be evaluated according to follow-up procedures described in Section 7.4.

The **start of the study** is defined as the date when the first patient in the study signs informed consent.

The **end of the study** is defined as the date of the last visit (including all follow-up visits) of the last patient in the whole study.

*CONFIDENTIAL*

### **5.3 Concomitant Medications**

Patients will be asked about prior medications during screening and instructed not to take any additional medications during the course of the study without prior consultation with the study team. At each visit, the patient will be asked about any new medications he or she is taking or has taken after the start of the study drug.

#### **5.3.1 Permitted Concomitant Medications**

Premedication with antiemetics is allowed according to standard practice guidelines after the DLT evaluation period in Part 1 if nausea and vomiting are observed post-dose during the DLT evaluation period.

Hematopoietic growth factors (G-CSF, GM-CSF) for treatment of neutropenia or transfusion of blood, red blood cells, and platelets may be used for prophylaxis after the DLT evaluation period (Day 1 to Day 21 in Cycle 1 [Part 1]) or for treatment based on the clinical judgment of the Investigator and as per local guidelines. (Note: GM-CSF is not approved in Japan).

Concomitant use of dietary supplements, medications not prescribed by the Investigator, and alternative/complementary treatments must be discussed with the Investigator.

Medical marijuana or other types of legally available cannabis products (e.g., CBD) are permitted as concomitant herbal medicines throughout screening, the treatment phase, and during the post-study follow up. If its use for palliative care began within a 7-day timeframe of study initiation, please discuss with the Medical Monitor.

Supportive care and other medications considered necessary for the patient's safety and well-being may be given at the discretion of the Investigator with the exception of those listed in Section 5.3.2.

#### **5.3.2 Prohibited Concomitant Treatments**

The following treatments are prohibited while in this study:

- Other investigational therapy
- Radiation therapy, except palliative radiotherapy on non-target lesions if deemed essential for symptomatic management at the Investigator's discretion.
- Anticancer surgery
- Other anticancer systemic therapy, including cytotoxic drugs, targeted agents, immunotherapy or endocrine therapy
- Prophylactic antiemetics and anti-diarrheal agents, or premedication for the prophylaxis of nausea, vomiting, and diarrhea are prohibited during DLT evaluation period (Day 1 to Day 21 of Cycle 1 [of Dose Escalation]).
  - Exception #1: patients, who at baseline, report their chronic and stable use of antiemetics or anti-diarrheal agents may continue use throughout the study. Changes in dose or frequency of use should be monitored and discussed with the Medical Monitor to determine if the change constitutes an adverse event

*CONFIDENTIAL*

- Exception #2: these medications may be administered for remedial therapy of symptoms after they have occurred at any time during the study, as well as for the prophylaxis of nausea, vomiting, and diarrhea after DLT evaluation period.
- Prophylactic administration of G-CSF (i.e., filgrastim, pegfilgrastim) or erythropoietin and transfusion of blood, RBCs, or platelets is prohibited within 14 days before the start of DS-6157a. Chronic therapy with erythropoietin at a stable dose that started at least 14 days before the first dose of DS-6157a may continue.
- The live flu vaccine (including the nasal mist version)
- Concomitant use of chronic systemic (IV or oral) corticosteroids or other immunosuppressive medications except for managing AEs (inhaled steroids or intra-articular steroid injections are permitted in this study).
  - Patients with bronchopulmonary disorders who require intermittent use of bronchodilators (such as albuterol) will not be excluded from this study.
- Concomitant treatment with any medication that is classified as having a known risk or possible risk of Torsades de pointes should be avoided from the start of study treatment through the end of Cycle 3 (see [www.crediblemeds.org](http://www.crediblemeds.org) and [Appendix E](#)). Consult with Medical Monitor if such medication is needed during the study.
- Concomitant treatment with chloroquine or hydroxychloroquine is not allowed during the study treatment. Refer to [Appendix H](#) for further details.

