Based on the safety data from the nonclinical studies and the ongoing study, ILD/pneumonitis and hepatotoxicity are important potential risks. Nausea and vomiting are classified as identified risks or adverse drug reactions. Other potential risks include IRR, other gastrointestinal events (i.e., diarrhea and colitis), hematological events (i.e., anemia, neutropenia, and thrombocytopenia), dermatological events, left ventricular ejection fraction (LVEF) decreased, renal events, and corneal events. These risks will be monitored closely in the DS-6157a clinical development program.

Although DS-6157a exhibits an acceptable safety profile, with close monitoring strategies in place, Daiichi Sankyo is further conducting a full analysis of all available dose escalation trial data to determine a dose level with a positive benefit-risk ratio. Further details are provided in the IB.

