9. Has a documented history of (non-infectious) interstitial lung disease (ILD)/pneumonitis that required corticosteroids, has current ILD/pneumonitis, or where suspected ILD/pneumonitis cannot be ruled out by imaging at screening.
10. Has a history of underlying pulmonary disorder, including but not limited to, pulmonary emboli within 3 months of the study randomization, severe asthma, severe COPD, restrictive lung disease, pleural effusion.
11. Has any autoimmune, connective tissue or inflammatory disorders (e.g., rheumatoid arthritis, Sjogren's, sarcoidosis) where there is documented, or a suspicion of pulmonary involvement at the time of screening.
12. Prior pneumonectomy
13. Has clinically significant pulmonary compromise or requirement for supplemental oxygen.
14. Has clinically significant corneal disease.
15. Has an uncontrolled infection requiring IV antibiotics, antivirals, or antifungals.
16. Has active human immunodeficiency virus (HIV) infection as determined by plasma HIV RNA viral load.
17. Has evidence of active hepatitis B virus (HBV) or hepatitis C virus (HCV) infection, as manifested by the detectable viral load (HBV-DNA or HCV-RNA, respectively).
18. Has received a live vaccine within 30 days prior to the first dose of study drug. Examples of live vaccines include, but are not limited to, the following: measles, mumps, rubella, varicella/zoster (chicken pox), yellow fever, rabies, Bacillus Calmette-Guérin (BCG), and

*CONFIDENTIAL*

typhoid vaccine. Seasonal influenza vaccines for injection are generally killed virus vaccines and are allowed; however, intranasal influenza vaccines (eg, FluMist®) are live attenuated vaccines and are not allowed.

19. Is a lactating mother (women who are willing to temporarily interrupt breastfeeding will also be excluded), or pregnant as confirmed by pregnancy tests performed within 7 days before the start of study treatment.
20. Women who plan to become pregnant while in the study and for at least 7 months after the last administration of study treatment.
21. Men who plan to father a child while in the study and for at least 4 months after the last administration of study treatment.

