## 6.1 Other Risks Associated with Drugs of the Same Class

MAAA-1181a is a derivative of exatecan (DX-8951f), a topoisomerase I inhibitor. Other products of the same class include irinotecan ([Irinotecan package inserts. 2016](#)) and topotecan ([Topotecan package inserts. 2015](#)). Exatecan is a camptothecin derivative, which has previously been developed by the former Daiichi Pharmaceuticals Co., Ltd. as an anti-cancer therapy.

The main risks associated with the use of topoisomerase I inhibitors include hematological toxicities and gastrointestinal toxicities. Hematological toxicities, manifesting as neutropenia, febrile neutropenia, anemia, thrombocytopenia, and pancytopenia are commonly observed. An increased risk of infections, including neutropenic colitis, neutropenic sepsis, and disseminated intravascular coagulopathy has been reported with these agents.

Diarrhea and delayed onset diarrhea, which can be severe and lead to dehydration, have been associated with topoisomerase I inhibitors. Other gastrointestinal toxicities include nausea, vomiting, ileus, and intestinal perforation. Acute cholinergic syndrome, manifesting as diarrhea and other cholinergic symptoms have been reported with irinotecan. Other significant risks include ILD, liver impairment, renal impairment, anaphylaxis, myocardial ischemic events, and thromboembolic events.

The safety profile of exatecan is broadly similar to the safety profile of other topoisomerase I inhibitors, with hematological toxicities and gastrointestinal toxicities being the most significant groups of events ([Cheverton et al. 2004](#), [Deciphera 2019](#), [De Jager et al. 2000](#)).

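### Any live vaccine is barred in the 30 days before first dose, but only the live flu vaccine is prohibited on study, so other live vaccines on treatment are left to consultation and Investigator discretion

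*Combined protocol and SAP*

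**What the plan says.** **At entry.** Criterion 18 in Section 3.2, repeated in the synopsis, excludes a patient who "Has received a live vaccine within 30 days prior to the first dose of study drug". It covers live vaccines in general. Its examples are expressly non-exhaustive and include measles, mumps, rubella, varicella/zoster and yellow fever. It allows injected seasonal influenza vaccine and rules out the intranasal form.

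**On study.** Section 5.3.2 opens with "The following treatments are prohibited while in this study". Its only vaccine item is "The live flu vaccine (including the nasal mist version".

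**General rules for everything else.** Under Section 5.3, patients are "instructed not to take any additional medications during the course of the study without prior consultation with the study team", and they are asked about new medications at each visit. Section 5.3.1 adds: "Concomitant use of dietary supplements, medications not prescribed by the Investigator, and alternative/complementary treatments must be discussed with the Investigator". It then says that supportive care and other medications judged necessary for safety and well-being "may be given at the discretion of the Investigator with the exception of those listed in Section 5.3.2".

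**Risks named in the protocol.** The potential risks of the treatment include "hematological events (i.e., anemia, neutropenia, and thrombocytopenia". Section 6.1 says of topoisomerase I inhibitors: "An increased risk of infections, including neutropenic colitis, neutropenic sepsis, and disseminated intravascular coagulopathy has been reported with these agents".

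**The concern.** The sponsor treats every live vaccine as a reason to keep a patient out for 30 days before dosing. After dosing starts, the express ban shrinks to one type. A patient who could not have entered after a recent measles or varicella vaccine could receive the same vaccine between cycles without breaching any listed prohibition.

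The stake is patient safety. The drug carries a listed risk of neutropenia, and its class carries a reported increase in infections, including neutropenic sepsis. Section 5.3.1 also makes the 5.3.2 list the limit of Investigator discretion, so what is missing from that list falls inside the discretion. Naming live flu vaccine alone may even lead a site to read other live vaccines as acceptable.

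**Working it through.** No arithmetic applies. The check sets the rules side by side and looks for any other rule that would close the gap.

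| Rule | Period | Live vaccines covered | Force |
|---|---|---|---|
| Section 3.2, criterion 18 | 30 days before first dose | All types | Exclusion |
| Section 5.3.2 | While in the study | Live flu only | Absolute prohibition |
| Section 5.3 | During the study | Any, if a vaccine counts as a medication | Prior consultation |
| Section 5.3.1, discussion rule | During the study | Any not prescribed by the Investigator | Discussion |
| Section 5.3.1, discretion rule | During the study | Any considered necessary and not listed in 5.3.2 | Investigator discretion |

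Other places where a wider ban might sit:

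1. Section 5.3.3 (restricted treatments) deals with tobacco products, e-cigarettes and vaping. It does not mention vaccines.
2. The prohibited list in Appendix H deals with chloroquine and hydroxychloroquine only.
3. Section 6 re-applies the exclusion criteria before intra-patient dose escalation. That reaches only selected Part 1 patients and is an eligibility check, not a bar on vaccination. Criterion 18 is also worded relative to the first dose of study drug.
4. Table 2 responds to low counts:
   - Grade 3 neutropenia delays the dose.
   - Grade 4 neutropenia and febrile neutropenia delay and reduce it.
   - Grade 4 lymphopenia delays it, and also reduces it by one level if resolution takes more than 14 days.
   - Grade 1 to 3 lymphopenia changes nothing.

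   These rules partly mitigate the underlying risk, but they govern when DS-6157a is given, not when a vaccine may be.

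None of these bars a live vaccine other than influenza after first dose.

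The protocol does match entry and on-study scope for some other items. Chloroquine and hydroxychloroquine have an entry washout (inclusion criterion 9) and an on-study ban in Section 5.3.2. Drugs with a known or possible Torsades risk appear with the same scope in exclusion criterion 1 and in Section 5.3.2. Matching scope is therefore familiar drafting here, though the protocol does not state it as a general principle.

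**The case against.** The strongest reply is that this is a preference about scope. Eligibility rules and concomitant-treatment rules serve different purposes, and nothing in the protocol says the second must mirror the first. The documents give no reason for criterion 18 and never link live vaccines to neutropenia or to this drug. The general rules also have substance: no additional medication should be taken before the study team is consulted, and that is the same team that applied criterion 18 at entry. A careful Investigator may well refuse. The number of patients with advanced GIST who would need another live vaccine is not given.

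Most of this stands as a limit on size. The harm argument is an inference, the consultation rule is a real prior gate, and the magnitude is unknown. It does not remove the gap. Consultation and discussion oblige people to talk but do not tell the study team what to answer, and the only list that would tell them names one live vaccine.

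A reader might infer more than the text supports:

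- *That Sections 3.2 and 5.3.2 contradict each other.* They do not. They cover different periods and can both be followed.
- *That the protocol approves other live vaccines on treatment.* It does not. It leaves them to general rules.
- *That the trial's results are compromised.* Nothing in the sample size, endpoints, dose-escalation rules or analyses depends on this item.

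**Conclusion.** The point holds as a minor patient-safety gap. The on-study prohibition is drawn more narrowly than the pre-dose one: all live vaccines before first dose, live influenza only afterwards. This is a stated rule that is too narrow, not a missing detail, and correcting it is a cheap improvement and not a necessity.

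Two assumptions carry the conclusion. First, a live vaccine is taken to be at least as much a concern during treatment as in the 30 days before it. That is inferred from the sponsor's own entry rule and live-flu ban, read with the listed neutropenia risk and the class infection risk; the documents do not state it. Second, a vaccine is taken to count as a medication under Sections 5.3 and 5.3.1. If it does not, the general controls are weaker than described here. The frequency of the problem cannot be estimated from the documents.

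**What to change.** Under the existing heading of Section 5.3.2, replace the live-flu bullet with: *Live vaccines of any type (including, but not limited to, the live flu vaccine and its nasal mist version).* Keep the heading's period and add no exception. Criterion 18 stays as it is.

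A route for medically necessary live vaccines, with dosing interrupted and then resumed as in the Appendix H chloroquine rule, is tempting but should not be added in this form. It would put an exception into a live-flu ban that is now absolute. The chloroquine rule also depends on a washout of more than 14 days before resumption, and the documents give no basis for a corresponding interval after a live vaccine.

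The change is one bullet at the next amendment, with no effect on visits, data collection, sample size or analysis. The downside is that a patient who needs another live vaccine must defer it or stop study treatment. How long the bar lasts after stopping depends on how the heading's period is read, a question the current live-flu bullet already raises.

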### 5.3.3 Restricted Concomitant Treatments

Use of tobacco products, e-cigarettes and vaping is strongly discouraged but not prohibited.

## 6. DOSE MODIFICATIONS

If toxicity occurs, the toxicity will be graded using the NCI [CTCAE Version 5.0](#), and appropriate supportive care treatment will be administered to decrease the signs and symptoms thereof. Dose adjustments will be based on the organ system exhibiting the greatest degree of toxicity.

The Investigator will evaluate which toxicities are attributed to the study drug and adjust the dose of the drug as recommended below. All dose modifications must be based on the worst preceding toxicity (CTCAE version 5.0).

Specific criteria for interruption, re-initiation, dose reduction, and/or discontinuation of DS-6157a are listed in [Table 2](#). All interruptions or modifications must be recorded on the AE and drug administration CRFs. Appropriate clinical experts must be consulted as deemed necessary.

There will be no dose modifications for Grade 1 or Grade 2 AEs unless specified below in [Table 2](#). For a recurrent Grade  $\geq 3$  AE, the patient will be permanently discontinued from study treatment based on Investigator discretion.

Prophylactic or supportive treatment for expected toxicities, including management of TEAEs, will be at the treating physician's discretion and per institutional guidelines, except for prophylactic treatment prior to the DLT evaluation period.

*CONFIDENTIAL*

Two dose reductions will be permitted (the dose cannot be reduced to <1.6 mg/kg) in any patient. Once the dose of DS-6157a has been reduced because of toxicity, all subsequent cycles must be administered at that lower dose level unless further dose reduction is required. More than 2 dose reductions are not allowed and the patient will be withdrawn from the study treatment if further toxicity meeting the requirement for dose reduction occurs.

During the dose escalation part of the trial, intra-patient dose escalation (IPDE) of DS-6157a may be allowed on a case by case basis in patients who may benefit from IPDE based on the clinical judgement of the investigator and in agreement with the Medical Monitor and Sponsor. The eligibility criteria for consideration of patients for IPDE are the following:

- Patient must provide consent for IPDE.
- A minimum of 4 cycles of treatment and evaluations must be completed before IPDE
- Patient must meet inclusion criteria of #1-3, 6 and 8 based on the most recent data, and 9 (except for DS-6157 treatment) again. Any criteria that did not meet the eligibility can be re-tested.
- Patient who meets any of exclusion criteria based on the most recent data, or who experienced ILD of any grade or any other dose modification toxicity event during DS-6157a treatment will not be eligible for IPDE.

IPDE may be conducted up to a dose that is 1 dose level below the dose already established to be safe and tolerable. Dose escalation should not be more than 3 dose levels at a time. The actual dose level will be decided based on the overall individual clinical status and PK profile. A patient may be allowed further IPDE after completing a minimum of another 4 cycles after the first IPDE, as long as the conditions for IPDE are met. AEs arising after IPDE should follow dose modifications/reductions per [Table 2](#), but further re-escalations will be prohibited after such events.

Dose can be delayed for up to 28 days from the planned date of administration. If a patient has a persisting AE/SAE that requires a longer dose delay, then patient will be withdrawn from the study after consulting with Medical Monitor.

Treatment cycles for a patient for whom DS-6157a dosing was temporarily withheld for any reason may have future cycles scheduled based on the date of the last DS-6157a dose. However, the tumor assessments will follow the pre-specified schedules relative to the start of the study treatment (Cycle 1 Day 1).

Investigators may contact the Medical Monitor or designee to discuss questions regarding dose modification or discontinuation of study drug.

All confirmed or suspected coronavirus disease 2019 (COVID-19) infection events must be recorded in the eCRF. Please refer to [Appendix H](#) for additional information on dose modifications.

*CONFIDENTIAL*

